6.1.3 Post-Treatment Period

After discontinuation of treatment with ISIS 420915, patients will enter the 3-month post-treatment evaluation period. This period consists of clinic and non-clinic visits for safety monitoring as outlined in the Schedule of Procedures (Appendix A and C). Weekly platelet and every 2-3 week serum creatinine testing is required for a minimum of 6 weeks after the last dose of Study Drug (this includes early termination patients as well as patients that complete the full treatment period). Patients that terminate treatment early and do not withdraw consent should have the post-treatment visit Week 169 conducted 3 months after the last dose of Study Drug. The 3-month post-treatment evaluation period may be omitted if the patient discontinues treatment in this study, but is continuing to receive treatment with ISIS 420915 via another mechanism.

6.2 Additional Study Assessments

6.2.1 Laboratory Assessments

Laboratory analyte samples will be collected throughout the study. A list of these analytes is contained in Appendix B.

6.2.2 Congestive Heart Failure

Any patient who develops signs, symptoms, or test results suggestive of new onset or worsening (if pre-existing) congestive heart failure should have the following evaluations performed (in addition to any tests deemed to be necessary by the attending physician) as soon as possible and the Investigator should consider referral to a cardiologist:

- Chest x-ray
- 12 lead ECG
- Echocardiogram

In addition the Congestive Heart Failure supplemental eCRF pages should be completed in the eCRF.

6.2.3 Arrhythmias

Any patient who develops signs, symptoms, or test results suggestive of new cardiac arrhythmia should have the following evaluations performed (in addition to any tests deemed to be necessary by the attending physician) as soon as possible and the Investigator should consider referral to a cardiologist:

- 12 lead ECG
- Echocardiogram

In addition, the Arrhythmias supplemental eCRF pages should be completed in the eCRF.

6.2.4 Myocardial Ischemia

Any patient who develops signs, symptoms, or test results suggestive of myocardial ischemia should have the following evaluations performed (in addition to any tests deemed to be necessary by the attending physician) and the Investigator should consider referral to a cardiologist:

- Serial 12 lead ECGs
- Serial cardiac enzyme evaluation (CKMB, cardiac troponin I or cardiac troponin T)

In addition, the Myocardial Infarction supplemental eCRF pages should be completed in the eCRF.

6.2.5 Event-Specific Supplemental eCRF Pages

In the event of any of the following, the corresponding supplemental eCRF pages should be completed in the eCRF:

- Death
- Valvulopathy (i.e., signs, symptoms or test results suggestive of impairment of function of 1 or more cardiac valves)
- Deep vein thrombosis or pulmonary embolism
- Peripheral arterial thromboembolism
- Cerebrovascular event or transient ischemic attack
- Revascularization
- Pulmonary hypertension

6.3 Restriction on the Lifestyle of Patients

6.3.1 Contraception Requirements

All patients of childbearing potential must refrain from sperm/egg donation and practice effective contraception from the time of signing the informed consent form until at least 3 months after their last dose of ISIS 420915.

For the purposes of this study, a woman of childbearing potential is defined as any female who has experienced menarche and who does not meet 1 of the following conditions:

- Postmenopausal: 12 months of spontaneous amenorrhea in females > 55 years of age or, in females ≤ 55 years, 12 months of spontaneous amenorrhea without an alternative medical cause and FSH levels in the postmenopausal range for the laboratory involved
- 6 weeks after surgical bilateral oophorectomy with or without hysterectomy
- Post hysterectomy

For the purposes of the study, effective contraception is defined as follows:

For male patients:

• Effective male contraception includes a vasectomy with negative semen analysis at follow-up, or the use of condoms together with spermicidal foam/gel/film/cream/suppository. Male patients must also encourage their female partner to use effective contraception from the time of signing the informed consent until 3 months after the patient's last dose of ISIS 420915. Effective contraceptive for the female partner includes surgical sterilization (e.g., bilateral tubal ligation), hormonal contraception, intrauterine contraception/device, or barrier methods (female condom*, diaphragm, sponge, cervical cap) together with spermicidal foam/gel/film/cream/suppository. Male patients with partners who are pregnant must use condoms to ensure that the fetus is not exposed to ISIS 420915.

For female patients:

- Using 2 or more of the following acceptable methods of contraception:
 - o Surgical sterilization (e.g., bilateral tubal ligation)
 - Hormonal contraception
 - Oral contraceptive (either combined or progestogen alone)
 - Injectable progestogen
 - Implants of etonogestrel or levonorgestrel
 - Percutaneous contraception/device
- Intrauterine contraception/device
- Combination of male condom* with female diaphragm together with spermicidal foam/gel/ film/cream/suppository

*Note: A female condom and a male condom should not be used together as friction between the two can result in either product failing.

6.3.2 Other Requirements

All patients will be required to fast for at least 8 hours before a blood sample is taken for the chemistry panel, PD and retinol assessments.

7. STUDY DRUG

7.1 Study Drug Description

ISIS 420915 characteristics are listed in Table 1.

ISIS 420915 is contained in stoppered glass vials or glass prefilled syringes (PFS) and will be provided to the Study Center by the Sponsor. The ISIS 420915 storage and preparation instructions will be provided by the Sponsor. For long-term storage at clinical sites, ISIS 420915 must be stored securely at 2° to 8° Celsius and be protected from light.

Table 1 Study Drug Characteristics

Study Drug	ISIS 420915
Strength	200 mg/mL
Volume/Formulation	1.5 mL solution per 3 mL vial Or
Route of Administration	1.5 mL solution per prefilled syringe SC 1.5 mL

7.2 Packaging and Labeling

The Sponsor will provide the Investigator with packaged ISIS 420915 labeled in accordance with specific country regulatory requirements.

7.3 Study Drug Accountability

The study staff is required to document the receipt, dispensing, and return/destruction of ISIS 420915 supplies provided by the Sponsor. The Study Center must return all used and unused ISIS 420915 vials to the Sponsor or designee. All used syringes must be disposed of as per the site's hazardous waste destruction policy.

8. TREATMENT OF PATIENTS

8.1 Study Drug Administration

For each individual patient, ISIS 420915 will be administered SC as a single 1.5 mL injection once-weekly for Weeks 1 to Y5-W52. ISIS 420915 may be administered by the Study Center personnel or at home by the patient/caregiver. If ISIS 420915 is administered during a clinic or non-clinic visit, all blood samples should be drawn prior to administration. It is not necessary for ISIS 420915 to be administered during clinic visits. Ideally blood draws should occur 7 days after the previous dose. If needed, dosing instructions and training will be provided to the patient/caregiver by the Study Center personnel.

If needed for tolerability reasons, the single 1.5 mL injection may be administered as 2 injections of smaller volume, but prior discussion with the Study Medical Monitor is encouraged.

Please refer to the Study Drug Manual provided by the Sponsor for more detailed instructions for ISIS 420915 preparation and administration.

8.2 Other Protocol-Required Drugs

All patients will take daily oral supplemental doses of the RDA of vitamin A (approximately 3000 IU or the closest approximate dose as available in the region where the patient resides). Commercially available vitamin A as a single supplement or as part of a multivitamin will be provided by the Study Center or designee, in accordance with local regulatory requirements and availability. The vitamin A supplement should be taken throughout the treatment and post-treatment evaluation periods.

8.3 Other Protocol-Required Treatment Procedures

There are no other protocol-required treatment procedures.

8.4 Treatment Precautions

No specific treatment precautions are required for this study.

8.5 Safety Monitoring Rules

Please refer also to the "Guidance for the Investigator" section of the Investigator's Brochure.

In addition to the standard monitoring of clinical safety parameters, the following guidelines are provided for the monitoring of selected parameters chosen based on preclinical and clinical observations.

Confirmation Guidance: At any time during the study (treatment or post-treatment periods), the initial clinical laboratory results meeting the safety monitoring or stopping criteria presented below **must be confirmed** by performing measurements (ideally in the same laboratory that performed the initial measurement) on new specimens. All new specimen collections should take place as soon as possible (ideally within 3 days of the initial collection).

Stopping Rule Guidance: In the event of an initial clinical laboratory result that meets a stopping criterion, patients must not be re-dosed until a confirmatory test result has been reviewed by the Study Medical Monitor. If any of the stopping criteria described in Section 8.6 are met and are confirmed, the patient will be permanently discontinued from further treatment with ISIS 420915, evaluated fully as outlined below and in consultation with the Study Medical Monitor or appropriately qualified designee, and will be entered into the post-treatment evaluation period of the study (after completing the early termination [ET] assessments). In general, patients who do not meet the stopping rules based upon retest may continue dosing. However, the Investigator and the Study Medical Monitor (or appropriately qualified designee) should confer as to whether additional close monitoring of the patient is appropriate.

Additional Guidance: If possible, a pharmacokinetic sample should be collected as soon as possible after an SAE has occurred (preferably within 2 weeks). In addition, if a patient is asked

to return to the clinic for additional evaluations due to an AE, then a pharmacokinetic sample should be taken at the time of the unscheduled visit.

For all safety monitoring rules below "baseline" will be defined as the ISIS 420915-CS3 Day 1 value.

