To ensure maintenance of the study blind in the ongoing ISIS 420915-CS2 study, TTR, RBP4, retinol, and NT-proBNP from the first 13 weeks of treatment in this study will not be available to the Sponsor, Investigators, Study Center Personnel, or the patients until the ISIS 420915-CS2 study is unblinded.

The mNIS+7 assessment will be conducted at Weeks 26, 52, 78, 104, 130, and 156. The NIS assessment will be conducted at Y4-W52 and Y5-W52. The Norfolk QOL-DN questionnaire is conducted at Weeks 26, 52, 78, 104, 130, 156, and Y4-W52 and Y5-W52. The Norfolk QOL-DN questionnaire should be the first assessment performed at these visits. If ISIS 420915 administration, ERG, or ophthalmology examinations are to be performed on the same day as an mNIS+7 or NIS assessment, they should be performed after the mNIS+7 or NIS assessment is complete. For Week 78 and Week 156 visits, 2 mNIS+7 assessments will be performed on separate days. A maximum of 2 weeks from the visit (Week 78 or Week 156) will be allowed to complete both assessments.

For Weeks 4-52 there is a \pm 7-day visit window. After Week 52 the visit window is \pm 10-day. All reasonable attempts should be made to ensure compliance with the visit schedule as outlined in the schedule of procedures (Appendix A). However, if a visit does not occur or is delayed, all subsequent visits should be calculated based on the time elapsed since Day 1 rather than from the date of the previous visit.

The Study Day 1 ECHO can be done any time in the screening period or up to 2 weeks after Day 1. The Day 1 ECHO is not done if the Week 65 ECHO was conducted in ISIS 420915-CS2. A \pm 2-week window is given for all other ECHOs.

During the treatment period, an ophthalmology examination will be performed at Weeks 26, 52, 78, 104, 130, 156, and 2 times in each subsequent year (26^{th} and 52^{nd} week of each year). An ERG examination will be performed at Weeks 78 and 156. A window of \pm 2 weeks is allowed for these eye examinations. Early termination ERG and ophthalmology examinations are only done if the patient discontinues treatment after \geq 9 months of dosing or unless deemed necessary by Investigator or Study Medical Monitor.

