8.5.3 Safety Monitoring Rules for Ocular Effects

All patients should receive an ophthalmology examination by an eye specialist at Weeks 26, 52, 78, 104, 130, and 156 and twice each subsequent treatment year (26th and 52nd week of each year). An ERG will also be performed at Weeks 78 and 156. In addition, any patient who complains of persistent ocular symptoms compatible with vitamin A deficiency (e.g., night blindness or dry eyes) should be referred for an ophthalmology examination. If the ophthalmologist confirms the patient's symptoms are consistent with vitamin A deficiency and/or the examination reveals physical findings that are consistent with vitamin A deficiency (but do not reach the stopping rule criteria described in Section 8.6.4) then an ERG examination should be conducted and analyzed by the central reader. In addition, it is suggested that a review

Amendment 5

of diet and supplement use and an evaluation for factors which may contribute to low vitamin A

If an ERG is changed from baseline and shows clear signs of vitamin A deficiency as assessed by the central reader and described below, then the patient should be monitored more frequently. Frequency will be determined by the Study Medical Monitor in consultation with the Investigator and ophthalmologist.

levels such as infection, alcohol consumption, and zinc and/or iron deficiency be conducted.

Clear signs of vitamin A deficiency as assessed by ERG include:

a. Change from baseline > 50%, and

Protocol

- b. Values below normal range (if baseline values were within normal range), and
- c. Changes that are approximately symmetrical between eyes (unless there is an alternative explanation for asymmetry)

Dosing with Study Drug may continue while these evaluations are being performed.

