8.6.3 Stopping Rule for Platelet Count Results

In the event of a confirmed platelet count less than 75,000/mm³, and in the presence of major bleeding or clinically-relevant non-major bleeding (defined below; Schulman et al. 2005), dosing of a patient with ISIS 420915 will be stopped permanently. The follow-up schedule for any

^{*} baseline is study CS3 Day 1 value

events meeting this stopping criterion will be determined by the Investigator in consultation with the Study Medical Monitor.

In the event of a confirmed platelet count less than $75,000/\text{mm}^3$, and in the absence of major bleeding or clinically-relevant non-major bleeding, further dosing of a patient with ISIS 420915 must be held until the platelet count returns to at least $100,000/\text{mm}^3$. Weekly platelet monitoring should continue during this period. In addition, the Investigator should give consideration to collecting duplicate platelet samples for study in a local lab in parallel to the central lab if it would provide quicker access to the patients platelet count. If the platelet count was confirmed to be $< 50,000/\text{mm}^3$, then monitoring should be increased to daily until two successive values show improvement. The Investigator must notify the Study Medical Monitor within 24 hours of any local lab platelet results that show a level $< 50,000/\text{mm}^3$.

The suitability of the patient for continued dosing and the need for any modification to treatment schedule or dose (refer to Section 8.7) will be determined by the Investigator in consultation with the Study Medical Monitor and will be based on factors such as the original rate of decline in the patient's platelet count, whether any bleeding events were experienced by the patient, and the speed of recovery of platelet count upon holding of dosing.

Definition of major bleeding events:

International Society on Thrombosis and Haemostasis (ISTH) Major Bleeding:

- 1. Fatal bleeding, and/or
- 2. Symptomatic bleeding in a critical area or organ, such as intracranial, intraspinal, intraocular, retroperitoneal, intraarticular or pericardial, or intramuscular with compartment syndrome, and/or
- 3. Bleeding causing a fall in hemoglobin level of 20 g/L (1.24 mmol/L) or more within 24 hours, or leading to transfusion of 2 or more units of whole blood or red cells

Definition of clinically-relevant, non-major bleeding events:

- 1. Multiple-source bleeding
- 2. Spontaneous hematoma $> 25 \text{ cm}^2$

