8.6.4 Stopping Rule for Ocular Effects

A patient should be permanently discontinued from Study Drug if an ERG is changed from baseline and shows clear signs of vitamin A deficiency (as described in Section 8.5.3) and an

ophthalmology examination reveals significant changes from baseline in any 1 of certain physical signs (Bitot's spots, xerophthalmic ulcers, keratomalacia, or other signs and symptoms of corneal necrosis) and a consultation with the central reader has occurred.

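### Protocol 8.5 ties the ERG criteria to a CS3 Day 1 baseline, but no ERG is scheduled at CS3 screening or Day 1

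*Combined protocol and SAP*

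**What the plan says.** - **Baseline for the rules.** Protocol 8.5 states that, for every safety monitoring rule that follows, baseline "will be defined as the ISIS 420915-CS3 Day 1 value". It makes no exception for eye tests.
- **ERG criteria.** Protocol 8.5.3 lists three signs that together mark an ERG as showing vitamin A deficiency. The first is "Change from baseline > 50%, and" and the second is "Values below normal range (if baseline values were within normal range), and". The third asks for approximate symmetry between the eyes.
- **Consequence of meeting them.** The patient is monitored more often. Section 8.5.3 adds: "Dosing with Study Drug may continue while these evaluations are being performed".
- **Schedule.** Protocol 6.1.2 says: "An ERG examination will be performed at Weeks 78 and 156". The ERG row of Appendix A agrees. Beyond these there are only symptom-triggered ERGs (8.5.3) and, in some cases, early-termination ERGs. The first scheduled CS3 ophthalmology examination is at Week 26.
- **Stopping rule.** Protocol 8.6.4 begins: "A patient should be permanently discontinued from Study Drug if an ERG is changed from baseline". It takes its definition of the ERG signs from 8.5.3. It also requires that an "ophthalmology examination reveals significant changes from baseline in any 1 of certain physical signs", and that the central reader has been consulted.

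**The concern.** A rule based on change from baseline can be applied only if the named baseline exists. Here the protocol names the CS3 Day 1 value and schedules no ERG at or before that day in CS3. Taken literally, the ERG criteria of 8.5.3 can never be shown to be met, and neither can the ERG condition of 8.6.4.

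In practice someone would reach back to a CS2 examination, but the text does not say which one. For a patient on active drug in CS2, it could be the examination before treatment or a later one on drug, if one was done. The two could answer the 50% question differently.

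The test matters because retinol reduction is an expected consequence of lowering TTR (Protocol 2.3.4), and ocular events related to vitamin A deficiency are an adverse event of special interest (SAP 3.3.2.1). There is also a reporting side. SAP 3.3.6 summarises ERG change from what the SAP calls the ISIS 420915 baseline, and it tabulates patients who reach the ocular stopping rule. The report would set counts from a rule tied to one baseline beside changes measured from another.

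**Working it through.** The plan gives no figure to reproduce. The check sets the provisions side by side.

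**1. What the rule needs.** Write B for the baseline ERG value and X for the current one.

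- Criterion a compares 100 × (B − X) / B with 50. It has no value without B.
- Criterion b applies only if B was within the normal range. Without B, that condition cannot be checked.
- Criterion c does not name a baseline.

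So 2 of the 3 criteria need B. They are joined by *and*, so the set cannot be shown to be met when B is missing.

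**2. What CS3 collects.**

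| Examination | At screening or Day 1 | First scheduled CS3 visit | Earliest day with the 2-week window |
|---|---|---|---|
| ERG | none | Week 78 (Day 540) | 540 − 14 = 526 |
| Ophthalmology | none | Week 26 (Day 176) | 176 − 14 = 162 |

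The list of screening assessments in SAP 2.1 also contains neither examination. No visit window brings either one near Day 1.

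**3. Whether any text supplies a substitute.**

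| Provision | What it does | Does it supply B? |
|---|---|---|
| Protocol 6.1.1 and Appendix A footnote 3 | CS2 results within 4 weeks may serve for screening evaluation | No: ERG is not a screening item |
| Appendix A footnote 5 | Window and early-termination conditions for eye examinations | No |
| Appendix A footnote 12 | Lets a CS2 Week 65 ECHO replace the Day 1 ECHO | No: ECHO only |
| Protocol 10.4 | Baselines for the final analysis | No: limited to that analysis |
| SAP 3.2.1.1.2 | Parent-study, OLE and ISIS 420915 baselines | No: analysis definitions, not monitoring rules |

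Footnote 12 shows that the authors wrote a carry-over where they wanted one. There is none for ERG.

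**4. How far this reaches into 8.6.4.** The sentence in 8.5 speaks of monitoring rules, and 8.6 is a separate set of stopping rules. Section 8.6.4 does not itself say Day 1. Its ERG limb is affected because it imports the 8.5.3 criteria. Its eye-sign limb asks for change from baseline and identifies none. By contrast, the renal stopping rule in 8.6.2 carries its own footnote: "baseline is study CS3 Day 1 value".

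**5. Whether an earlier reference exists.** SAP 3.2.1.1.2 accepts CS2 baseline ERG and ophthalmology examinations done up to one week after CS2 Day 1. SAP 3.2.1.1.4 defines an on-treatment ERG period for the parent study, but the CS2 visit schedule is not in these documents. A parent-study baseline was therefore provided for. Whether a later CS2 ERG was scheduled cannot be told.

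**The case against.** The best defence is that the sentence in 8.5 is general wording written with laboratory tests in mind. The authors repeated the Day 1 baseline where it matters for renal function (8.5.2 and 8.6.2) and did not repeat it in 8.5.3. The ERG is assessed by a central reader, who must also be consulted before a stop, so the comparison is not made separately at each site. Section 8.5 refers to guidance in the Investigator's Brochure, and sponsor safety review follows a Safety Management Plan. Neither is available here, and either might name the comparator. The consequences are also small. Section 8.5.3 alone changes only how often the patient is seen. Patients with persistent symptoms are referred for examination at any time, and Section 8.8 still allows discontinuation for an adverse event.

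Most of this stands, and it limits the impact. It does not remove the defect. The sentence covers all the rules below it without exception, and 8.5.3 is one of them. A central reader makes the comparison consistent only if the reader's comparator is fixed, and the protocol fixes one that is not collected. If another document names a CS2 examination, it contradicts the protocol as written.

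**Conclusion.** The point holds as a drafting error in the rule. Section 8.5 gives the ERG criteria a baseline that CS3 does not collect: no ERG is scheduled at screening or Day 1, and 2 of the 3 joined criteria depend on one. The ERG limb of 8.6.4 is affected through its cross-reference, and the eye-sign limb lacks a named baseline. It is worth correcting, with limited practical impact.

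Three stronger readings are tempting, and the documents do not support them.

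- **A reader might infer that no reference ERG exists, so the ocular stop cannot work.** The SAP shows that a parent-study baseline examination was provided for. The rule points to the wrong examination.
- **A reader might infer that 8.6.4 itself prescribes Day 1.** It names no baseline.
- **A reader might measure the harm by the doses given before Week 78, or by how far an on-drug CS2 comparator would shift the 50% threshold.** The dose count restates the schedule and ignores symptom-triggered ERGs. The shift needs a CS2 ERG schedule and an amount of ERG loss, and the documents give neither. A shift in criterion a need not change the result either, because b and c must also hold.

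The conclusion rests on the protocol and SAP alone. It assumes that patients have the parent-study baseline examination that the SAP describes.

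**What to change.** Add to 8.5.3 and repeat in 8.6.4:

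> For ERG and ophthalmology examinations, baseline is not the CS3 Day 1 value. It is the parent-study baseline examination for patients on active drug in CS2 (as for the safety analysis), and the last parent-study examination before CS3 Day 1 for patients on placebo in CS2, whatever its age.

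Do not call this the ISIS 420915 baseline. For former-placebo patients the SAP equates that term with the OLE baseline, which is missing when no assessment falls within 90 days before CS3 Day 1. State that the difference is intended for safety monitoring, so that one term does not carry two meanings.

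For former-active patients, using the pre-treatment examination is a real choice. A later CS2 examination, if there is one, would lie closer to Day 1 but would build any change already caused by the drug into the reference.

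The cost is small. No new examination is needed and the SAP's analysis definitions can stay as they are. The reference examination may be old. The change needs a protocol amendment and, because it touches a stopping rule, probably regulatory and ethics approval under Protocol 12.1.
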